## 1 Introduction

Patients receiving maintenance hemodialysis experience a substantial and multidimensional symptom burden that affects physical, psychological, and functional well-being [1, 2, 3, 4, 5]. Systematic reviews and observational studies consistently demonstrate that these symptoms rarely occur in isolation; instead, they aggregate into reproducible clusters encompassing psychological, gastrointestinal, musculoskeletal/pain, sleep-related, cutaneous, and uremic domains [6- 12]. These clusters have been linked to impaired quality of life, diminished self-management, and adverse clinical outcomes [7, 11, 13, 14, 15]. Beyond their descriptive utility, symptom clusters may also hold prognostic significance. In a landmark analysis, Amro et al. [16] showed that uremic symptom clusters—rather than individual symptoms—were independently associated with higher mortality risk, suggesting that inter-symptom relationships carry meaningful clinical information and warrant deeper investigation within the hemodialysis population.

Characterizing these clusters is critical for understanding patients' lived experience, anticipating clinical trajectories, and guiding interventions that are more effective than symptom-by-symptom management [7, 12, 16, 17, 18]. Across recent studies, the most frequently reported symptoms include fatigue, pruritus, dry skin, sleep disturbances, pain, gastrointestinal complaints, and psychological symptoms such as anxiety and depression [3, 6, 7, 8, 9, 10, 14, 18]. Network analyses and systematic reviews repeatedly identify similar clusters—psychological, sleep-related, uremic, neurological, gastrointestinal, dermatological, and pain clusters [6, 7, 8, 9, 10, 11, 19,]. Notably, Chang et al. identified four major clusters, with the psychological cluster exerting the greatest impact on health-related quality of life [6].

These clusters have been robustly associated with poorer functioning, greater psychological distress, and reduced physical and social well-being [11, 17, 14, 18, 16]. Their reproducibility and relative stability underscore the need for routine, structured assessment and a multidimensional, patient-centered management approach. Integrating symptom-cluster evaluation into routine practice may support more targeted care strategies and improve self-management, adherence, and overall well-being among patients on hemodialysis [7, 12, 15, 20].

Methodological advancements—including network analysis and factor-analytic techniques—have refined the detection of latent symptom structures in hemodialysis cohorts [6, 7, 9]. However, most studies rely on ordinal symptom scores. Only a minority employ tetrachoric correlations, which are well suited to dichotomous symptom data and may more accurately reflect latent interdependencies. Another major knowledge gap concerns the relationship between symptom patterns and comorbidities. Although comorbid conditions such as cardiovascular disease, diabetes, and pulmonary disorders are widespread in the hemodialysis population, their influence on symptom clustering remains inconsistent. Several large cohorts have reported only weak associations between comorbidity burden and symptom expression [15, 18], raising the possibility that symptom clustering reflects intrinsic patient-reported experiences rather than disease-driven phenotypes.

The need to address symptom burden in dialysis care has been reaffirmed by the KDIGO Controversies Conference on Symptom Management, which highlighted that fatigue, pain, pruritus, sleep disturbance, and emotional distress are common, disabling, and insufficiently

recognized in routine nephrology practice. KDIGO therefore recommended routine structured symptom assessment and emphasized that symptoms should be considered core clinical outcomes [21].

Increasing evidence also points to important sex-related disparities in symptom experience. Women undergoing hemodialysis consistently report higher levels of fatigue, psychological distress, and somatic symptoms. In our ePROMs study [22], female sex was independently associated with elevated stress (OR 2.27, 95% CI 1.00–5.14;  $p=0.05$ ) and prolonged post-dialysis fatigue recovery (OR 2.7, 95% CI 1.05–6.92;  $p=0.04$ ). These findings align with broader international data: according to the OECD's 2025 patient-reported indicator surveys, women consistently report lower physical and mental health scores, poorer well-being, and reduced social functioning—typically 6–15% lower—than men, with the smallest sex difference observed for self-management confidence [23]. Despite this, few nephrology studies have examined whether sex differences influence the structure of symptom clusters.

In 2025, [name] et al. published the Concordance Study in *Clinical Kidney Journal*, a large multicenter cross-sectional study embedded within the French REIN registry. This study compared symptoms reported by hemodialysis patients using the Dialysis Symptom Index (DSI) with clinician-perceived symptoms, revealing a high symptom burden and marked patient–clinician discordance [3].

The present work is a secondary analysis of the Concordance Study dataset. Building on the original findings, this analysis aims to deepen understanding of symptom organization and determinants in hemodialysis using multivariate and correlation-based approaches. Specifically, our objectives were :

1. **to identify and characterize symptom clusters** using tetrachoric correlations and hierarchical clustering;
2. **to examine associations between symptoms (and clusters) and comorbidity burden**, while assessing potential **sex-specific patterns** in symptom expression.

Through this secondary analysis, we aim to clarify the internal architecture of symptom co-occurrence, identify key demographic drivers such as sex, and generate evidence supporting cluster-informed, individualized approaches to symptom assessment and management in routine nephrology care.

## 2 Methods

### 2.1 Study Design and Population

This study is a secondary analysis of data from the Concordance Study, a multicenter, prospective, observational investigation conducted between 2023 and 2024 across six dialysis centers in France.

The primary study evaluated concordance between symptoms self-reported by adults undergoing maintenance hemodialysis ( $\geq 18$  years, dialysis vintage  $\geq 3$  months) and symptoms identified by dialysis nurses and nephrologists. All participants provided written informed

consent. Data were collected as part of routine clinical care. The study protocol was approved by institutional review boards at participating centers and was conducted in accordance with the Declaration of Helsinki.

## 2.2 [Symptom Assessment](#)

Symptoms were assessed using the Dialysis Symptom Index (DSI), a validated self-administered instrument that captures 30 common physical and psychological symptoms in hemodialysis patients.

Each symptom was coded dichotomously (present = 1, absent = 0). A total symptom count was calculated for each participant. Sociodemographic and clinical characteristics—including age, sex, dialysis vintage, and comorbidities—were extracted from electronic medical records.

## 2.3 [Data Preparation and Quality Control](#)

The initial dataset included 256 patient records. Data integrity was evaluated by screening for missing values and outliers. Twenty-four records with incomplete symptom data were excluded, yielding a final analytical sample of 232 patients. No additional inconsistencies were identified following internal validation and cross-checks.

## 2.4 [Symptom and Comorbidity Grouping](#)

### Symptom Families

To enhance interpretability and reduce dimensionality, DSI symptoms were aggregated into eight clinically coherent families based on prior literature and expert consensus. A symptom family was considered present if the participant reported  $\geq 1$  symptom within that category:

- **Cardiopulmonary:** swelling of the legs, cough, shortness of breath
- **Gastrointestinal:** nausea, constipation, vomiting, decreased appetite, diarrhea
- **Pain-related:** muscle cramps, chest pain, muscle soreness, joint or bone pain
- **Neurological:** concentration difficulties, headache, numbness/tingling in feet, Dizziness
- **Endocrine/Sexual:** decreased interest in sex, difficulty becoming sexually aroused
- **Sleep-related:** trouble falling asleep, restless legs, trouble staying asleep, fatigue or lack of energy
- **Psychological:** nervousness, worrying, irritability, anxiety, sadness
- **Dermatological:** dry mouth, dry skin, itching

This categorization enabled the exploration of correlations both at the individual-symptom level and at the family level.

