## 2.5 [Symptom Frequency Analysis](#)

A univariate descriptive analysis was performed to quantify the frequency of individual symptoms and symptom families. This provided an overview of symptom burden and highlighted the most prevalent versus less common symptoms prior to exploring inter-symptom associations. Frequencies and proportions were summarized in tabular format, with descriptive comparisons by age, sex, and comorbidity status.

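### Scoring a symptom family as present on one or more symptoms makes family frequencies non-comparable across families of 2 to 5 items, and can cost substantial power in family-level association analyses

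*Protocol*

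**What the plan says.** Protocol section 2.2 states that the Dialysis Symptom Index "captures 30 common physical and psychological symptoms", codes each symptom as present or absent, and computes one total symptom count per patient. In section 2.4, "DSI symptoms were aggregated into eight clinically coherent families", for interpretability and lower dimensionality. The scoring rule follows: "A symptom family was considered present if the participant reported" at least one symptom in that category.

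The families differ in size. The endocrine/sexual family has two items ("decreased interest in sex, difficulty becoming sexually aroused"). The gastrointestinal family has five ("nausea, constipation, vomiting, decreased appetite, diarrhea"), as does the psychological family. The sleep-related family has four: "trouble falling asleep, restless legs, trouble staying asleep, fatigue or lack of energy". No per-family count, proportion or adjustment for item number is described.

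Three uses follow:
- family frequencies, with descriptive comparisons by age, sex and comorbidity status (section 2.5);
- the tetrachoric matrix for families (sections 2.6 and 2.9);
- correlation testing of families against binary comorbidity groups (section 2.4, Comorbidity Groups).

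Individual-symptom frequencies and correlations are kept alongside.

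**The concern.** A family with more items has more chances to be scored present. Two families whose symptoms are equally common will show different frequencies if one has two items and the other five, so a reader of the frequency table cannot separate family size from symptom burden.

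The rule also treats a patient with one psychological symptom like a patient with all five. In a large family of common symptoms most patients are scored present, the absent group becomes small, and the indicator carries little information about who has more symptoms.

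This bears on the second objective. The only comorbidity testing that the methods describe uses the family indicators. The Introduction raises the possibility that clustering does not reflect disease-driven phenotypes. A weak family–comorbidity correlation could then be read as support for that view when part of it comes from coarse scoring.

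**Working it through.** **Inputs from the protocol.** Family sizes, in the order listed: 3 + 5 + 4 + 4 + 2 + 4 + 5 + 3 = 30, which agrees with the 30 items in section 2.2. Analysed sample: 256 − 24 = 232, as stated in section 2.3.

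**Assumed inputs.** Item prevalence p, latent correlation r between items of a family, the size of the comorbidity group and the effect size. None of these is in the protocol.

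**Step 1: family prevalence.** Under an equicorrelated latent-normal model with t = Φ⁻¹(1 − p) and F standard normal,

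P(at least one of k) = 1 − E[ Φ( (t − √r·F) / √(1 − r) )^k ].

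With r = 0 this is 1 − (1 − p)^k. At p = 0.30 that gives 1 − 0.7² = 51% for two items and 1 − 0.7⁵ = 83% for five. At r = 0.4 and p = 0.50 the two-item case has a closed form: 1 − [1/4 + arcsin(0.4)/(2π)] = 1 − 0.3155 = 68%.

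| Item prevalence (r = 0.4) | 2 items | 5 items |
|---|---|---|
| 20% | 32% | 52% |
| 30% | 46% | 67% |
| 40% | 58% | 79% |
| 50% | 68% | 87% |

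The gap narrows as correlation rises but does not vanish. At p = 0.30 it is 47% versus 71% (r = 0.3), 44% versus 63% (r = 0.5) and 41% versus 55% (r = 0.7).

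**Step 2: the sleep family.** The Introduction lists fatigue first among frequently reported symptoms, and section 2.4 puts it in this family. If fatigue is at 75% and the other three items at 30–45%, the family is present in about 90% (r = 0.2) to 81% (r = 0.6). That leaves 232 × 0.10 ≈ 23 to 232 × 0.19 ≈ 44 patients absent. Fatigue would then be present in 0.75/0.90 = 83% to 0.75/0.81 = 93% of patients scored positive.

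**Step 3: power.** Simulation with n = 232, a 40% group, r = 0.4, a 0.35 SD latent shift on all items and a two-sided 5% test:

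| Family | At least one | Item count |
|---|---|---|
| 2 items at 30% | 64% | 73% |
| 5 items at 30% | 66% | 90% |
| 5 items at 40% | about 58% | 89% |
| 4 items at 50% | 48% | 87% |

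Repeat runs mostly agree within a point or two. The widest spread is for 5 items at 40%, where the present/absent power ranged from 54% to 61%, possibly because the chi-square was computed differently.

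**Step 4: where the loss is larger or absent.** With a rarer comorbidity (10%), a 0.4 SD shift, r = 0.3 and five items at 30%, power is 28% versus 69%. When one uncommon item carries the association (0.5 SD, 40% group, three items at 15%, r = 0.5), power is 32% versus 27%, slightly in favour of the present/absent rule.

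**The case against.** The strongest defence is that the rule is a literal and disclosed definition of having any symptom of a kind. The item lists are printed, the reason for grouping is given, and this is an exploratory secondary analysis with no powered family-level hypothesis. Individual-symptom frequencies and correlations are kept, fatigue appears there on its own, and the cluster objective can be served from individual items. All of this stands, and it confines the point to the family-level results.

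The defence also disposes of four stronger readings that a reader might infer:
- *Family prevalence is simply an artefact of item number.* Item prevalence and correlation matter as well. At r = 0.3 a 2-item family with items at 50% (70%) about equals a 5-item family with items at 30% (71%).
- *The rule discards most of the power.* In the four cases of Step 3 more than half remains: 48/87 = 55% in the worst and 64/73 = 88% in the mildest. A loss of more than half occurs only in part of the assumed range, such as the rare-comorbidity case (28/69 = 41%).
- *The plan ranks families.* The phrase "highlighted the most prevalent versus less common symptoms" in section 2.5 refers to symptoms. Families are only tabulated.
- *The sleep family is essentially a fatigue indicator.* That rests on assumed prevalences and cannot be established from the protocol.

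The defence does not remove the main point. Disclosing the item lists does not let a reader correct a frequency for family size. The total symptom count does not replace a per-family score. For comorbidity testing, section 2.4 names only the families.

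**Conclusion.** The point holds as a weakness of method, not as a contradiction or error in the protocol. Family frequencies under this rule are not comparable across families of different size: with equally common items and r = 0.4, item number alone produces a gap of 18 to 21 percentage points between two and five items (87 − 68 = 19 at 50%; 79 − 58 = 21 at 40%; 52 − 32 = 20 at 20%; the unrounded gap at 50% is just above 18).

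In family-level association analyses the loss of power against an item count ranges from about none (one uncommon item drives the association), through 9 points (2 items at 30%), to 24 points (5 items at 30%) and 39 points (4 items at 50%). It is substantial mainly for larger families of common symptoms, or where the comorbidity is rare.

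The direction follows from the stated rule and family sizes. Every magnitude depends on assumed prevalences, correlations and effects. Individual-symptom results are not affected.

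**What to change.** - For the family–family correlations (section 2.6), the family–comorbidity correlations (section 2.4) and the family comparisons by sex (section 2.5), score each family as the number or proportion of its items present. Use polychoric, polyserial or rank correlation as appropriate.
- Keep the present/absent frequency as a descriptive line, shown with the number of items in the family and a note that it is not comparable across families.
- Show the sleep-family result with and without fatigue.

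The binary items are already in the data set, so this is a re-coding with no new data collection. The cost is a slightly less simple table.

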### Comorbidity Groups

Comorbidities were categorized into major clinical domains to capture patterns of multimorbidity:

- **Cardiovascular:** ischemic cardiomyopathy or myocardial infarction, heart failure, peripheral arterial disease, stroke or transient ischemic attack, arrhythmias, abdominal aortic aneurysm
- **Pulmonary:** chronic respiratory failure or long-term oxygen therapy
- **Digestive:** cirrhosis or chronic liver disease
- **Endocrine/Diabetes:** diabetes mellitus (any type)
- **Cancer:** active malignancy

Each comorbidity group was treated as a binary variable (present/absent). This classification enabled correlation testing between symptom families and comorbidity profiles.

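### Objective 2 names only pairwise symptom–comorbidity correlations, which cannot separate comorbidity from age, sex or dialysis vintage, although all three are on record

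*Protocol*

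**What the plan says.** The second objective (Introduction) is "to examine associations between symptoms (and clusters) and comorbidity burden", together with possible sex-specific patterns. The Introduction says the work proceeds "using multivariate and correlation-based approaches".

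Section 2.4 makes both sides of the comparison binary. Symptoms are grouped: "DSI symptoms were aggregated into eight clinically coherent families based on prior literature and expert consensus", a family counting as present with at least one symptom. For the five comorbidity groups: "Each comorbidity group was treated as a binary variable (present/absent". The method then named is: "This classification enabled correlation testing between symptom families and comorbidity profiles".

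Section 2.2 lists the extracted characteristics, "including age, sex, dialysis vintage, and comorbidities". Section 2.5 uses age, sex and comorbidity status for descriptive comparisons only. Vintage enters no stated analysis, although the inclusion criterion in section 2.1 ("dialysis vintage $\geq 3$ months") sets no upper limit on it. Sections 2.6 and 2.9 describe tetrachoric correlations among symptoms and among families. Neither mentions comorbidity, a covariate or a regression model.

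**The concern.** A correlation between two binary variables has no place for a third. If age, sex or vintage relates both to having a comorbidity and to reporting symptoms, the coefficient carries their contribution too, and the reader cannot tell how much.

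The protocol supplies one side of that structure itself. From an earlier study of patient-reported outcomes it states that "female sex was independently associated with elevated stress (OR 2.27, 95% CI 1.00–5.14", and it gives an odds ratio of 2.7 for prolonged post-dialysis fatigue recovery.

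The interpretation at stake is also stated. The Introduction takes weak comorbidity associations in other cohorts as a sign that clustering may be intrinsic to patients' experience and not driven by disease. A coefficient of unknown bias is poor evidence for or against that idea. The word multivariate in the Introduction does not close the gap. The multivariate techniques that follow are hierarchical clustering and multiple correspondence analysis (section 2.8), and neither adjusts a symptom–comorbidity association.

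**Working it through.** **Figures in the protocol.** Sample: 256 − 24 = 232, as stated. The eight families contain 3 + 5 + 4 + 4 + 2 + 4 + 5 + 3 = 30 symptoms, as stated. Eight families by five groups gives 40 pairwise comparisons. The protocol gives no expected size for any symptom–comorbidity association, so there is no planned figure to reproduce. The two sex odds ratios agree with their intervals: SE = ln(5.14/1.00)/3.92 = 0.418 and z = ln(2.27)/0.418 = 1.96; SE = ln(6.92/1.05)/3.92 = 0.481 and z = ln(2.7)/0.481 = 2.06.

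**Model for illustration.** logit P(symptom) = α + ln(1.5)·C + γ·F, where C is comorbidity and F is female. Expected cells are summed over sex, weighted by the share of each sex and its comorbidity prevalence. Crude OR = (ad)/(bc), where a and b are symptom present and absent with comorbidity, and c and d the same without it.

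- From the protocol: γ = ln(2.27) or ln(2.7).
- Assumed, because the protocol does not give them: adjusted comorbidity OR 1.5, 40% women, symptom prevalence 50% in men without comorbidity, and comorbidity prevalence by sex (varied).

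**Sex alone, γ = ln(2.7).** Symptom probabilities are 0.500 and 0.600 in men without and with comorbidity, and 0.730 and 0.802 in women.

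- Comorbidity 60% in men, 40% in women: (0.3443 × 0.1849)/(0.1757 × 0.2951) = **1.23**.
- Comorbidity 50% in both, so no confounding: (0.3404 × 0.2041)/(0.1596 × 0.2959) = **1.47**. The gap from 1.50 is non-collapsibility of the odds ratio.
- Comorbidity 45% in men, 60% in women: (0.3545 × 0.2082)/(0.1555 × 0.2818) = **1.68**.

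With γ = ln(2.27) the same three settings give 1.27, 1.48 and 1.66.

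**Age added, γ = ln(2.27).** Assume half the patients are older, and a comorbidity prevalence of 40% in younger men.

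- Older patients: symptom OR 0.5, comorbidity OR 2.5; women: comorbidity OR 0.6. Crude OR **1.16**.
- Older patients: symptom OR 2.0, comorbidity OR 2.5; women: comorbidity OR 1.5. Crude OR **1.83**.
- If the adjusted OR is 1.0, these two settings give 0.79 and 1.24.

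**A second set of assumptions.** Symptom prevalence 35% in the reference men, and comorbidity 25 percentage points commoner in the older half.

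- Comorbidity 65% in men and 40% in women, sex OR 2.7, age–symptom OR 0.6: crude OR **1.02**.
- Comorbidity 55% and 50%, sex OR 2.27, age–symptom OR 0.6: crude OR **1.25**. Inverting only the age–symptom OR to 1/0.6 = 1.67 moves this to **1.60**, across the assumed 1.5.

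**Against sampling error and the protocol's labels.** With N = 232, 55% comorbidity and 45% symptom prevalence, the SE of the log OR is √[1/(232 × 0.55 × 0.45 × 0.55 × 0.45)] = 0.27, so an OR of 1.5 has a 95% interval of about 0.89 to 2.52. The shift to 1.16 is ln(1.50/1.16) = 0.26, about one SE. The shift to 1.02 is 0.39, more than one. An OR of 1.5 at 50% comorbidity corresponds to a tetrachoric coefficient of about 0.16, and 1.83 in the setting above to about 0.23. Both are weak under section 2.7 (below 0.3).

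**The case against.** The strongest reply has four parts.

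**The method is thinly described, and the rest may be in a statistical analysis plan.** Section 2.4 says what the grouping makes possible. It names no coefficient and no model, and section 2.9 omits comorbidity. That the analysis is unadjusted is inferred from the absence of covariates. This is fair, and a covariate list alone could be left to a later plan. But the protocol does name a method for a stated objective, and nothing in it points to adjustment.

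**Direction.** A reader might infer that objective 2 is confounded towards finding no role for comorbidity. The documents do not support that. They link sex to symptoms but give no link from age, sex or vintage to comorbidity, and none from age or vintage to symptoms. Changing one assumption reverses the direction. This part of the reply stands in full.

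**The weak-association reading.** A reader might also infer that confounding alone would produce the weak associations that the Introduction discusses. That does not follow either. The assumed association of 1.5 is already weak by the protocol's own cut-off before any confounding, and every modelled crude value stays weak.

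**Size.** The sex odds ratios come from another study with different outcomes, and their lower limits are 1.00 and 1.05. Most modelled shifts are no larger than sampling error. Both facts limit what can be said about size. They do not remove the point: a bias of unknown sign is not reflected in a confidence interval.

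**Conclusion.** The point holds as a limitation of the named method. Pairwise correlation cannot separate comorbidity from age, sex or dialysis vintage, and the protocol uses none of these for adjustment although it has them. It does not show that objective 2 is in fact confounded, nor in which direction.

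The illustrative range is a crude OR of about 1.0 to 1.8 for an assumed adjusted OR of 1.5, with roughly 0.02 to 0.03 of the gap due to non-collapsibility in the sex-only settings with equal comorbidity. Apart from the two sex–symptom odds ratios, every input is an assumption, and vintage could not be modelled for lack of any figure. The analysis is exploratory, so this is not fatal. It does bear on one of two stated objectives, and it can be remedied with data already held.

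**What to change.** In section 2.4 (Comorbidity Groups) and section 2.9, state that the main symptom–comorbidity analysis is a logistic model for each symptom family, and for each cluster once clusters are defined. The five comorbidity groups enter together, so that diabetes and cardiovascular disease, for example, are adjusted for each other. Age, sex and dialysis vintage are covariates, with age and vintage kept continuous. Use penalised (for example Firth) estimation where a comorbidity group, or the absence of a family, is rare. Report adjusted odds ratios with intervals, and keep the unadjusted correlations as description.

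The cost is protocol wording and eight family models plus one per cluster, all on existing data. Intervals will widen for rare groups: at 10% comorbidity and 80% symptom prevalence (assumed), even the unadjusted SE of the log OR is about 0.55. If a family is absent in 20% of patients (assumed), about 232 × 0.20 ≈ 46 patients lack it, against eight coefficients if each covariate takes one term. That is why penalised estimation should be named in advance.
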